9.1.2.1 Lesions that become too small to measure

As patients respond to treatment, target lesions may be too small to measure. The radiologist performing the tumor evaluation must provide clear documentation that the lesion is either 'present, but too small to measure' or must document that the lesion has in fact disappeared. In the case where the lesion has disappeared then the measurement would be recorded as 0 mm. However, in all cases the radiologist must make an attempt to provide an actual measurement of all target lesions, even if the lesion measures less than 5mm. In cases where the lesion is too small to measure and the radiologist cannot provide a measurement, a measurement of 5 mm will be documented.

9.1.2.2 Lesions that split or grow together

If a target lesion splits into two separate lesions, the lesion diameters need to be added together to calculate the sum of the lesions. If two target lesions grow together, the vector of the longest diameter of the now merged lesions will be recorded as the lesion measurement.

9.1.3 On-Study Tumor Imaging

Following the screening CT scans, patients are to have repeat radiological assessments at the end of Cycle 3 [9 weeks (63 days \pm 3 days) from Cycle 1 Day 1]. Subsequent radiological assessments are to be performed every 9 weeks (at the end of every 3rd treatment cycle) until documentation of disease progression. If cycles become delayed, for whatever reason, the imaging schedule will as a default follow a nine-week pattern regardless of where in terms of cycles the subject is. If there is a large mismatch the PI can discuss frequency with the medical monitor

Per RECIST 1.1, if a patient has a documented partial or complete response, a

confirmatory tumor radiological assessment is to be performed not less than 4 weeks from the date the response was first documented.

Patients are to continue to have tumor assessments performed until whichever of the following occurs first:

- Site-assessed disease progression is documented
- The start of new anti-cancer treatment
- Withdrawal of consent
- Death
- The end of the study

9.1.4 Immune RECIST (iRECIST)

RECIST 1.1 will be adapted to account for the unique tumor response characteristics seen with treatment of pembrolizumab. Immunotherapeutic agents such as pembrolizumab may produce antitumor effects by potentiating endogenous cancer-specific immune responses. The response patterns seen with such an approach may extend beyond the typical time course of responses seen with cytotoxic agents, and can manifest a clinical response after an initial increase in tumor burden or even the appearance of new lesions. Standard RECIST may not provide an accurate response assessment of immunotherapeutic agents such as pembrolizumab. Therefore, RECIST 1.1 will be used with the following adaptations:

- If radiologic imaging verifies initial progressive disease (PD), tumor assessment should be repeated ≥ 4 (iRECIST 4-8) weeks later in order to confirm PD with the option of continuing treatment per below while awaiting radiologic confirmation of progression.

At initial progressive disease based on RECIST 1.1 criteria, iRECIST: can have iUPD (Unconfirmed Progressive Disease). Imaging must then be repeated 4-8 weeks later. Progression is defined as the time of the first iUPD followed by the next confirmatory scan showing progression. Thus, iPFS is defined as the time to iUPD if the next scan (4-8 weeks later) confirms PD (state change from iUPD to iCPD, time to progression defined in this instance as iUPD). Note: following iUPD, if the next assessment is not a CPD, treatment can continue until iCPD is documented.

- iRECIST criteria:
 - For iUPD; if repeat imaging shows $< 20\%$ tumor burden increase compared to nadir, stable or improved previous new lesion (if identified as cause for initial PD), and stable/improved non-target disease (if identified as cause for initial PD), treatment may be continued/resumed.
 - NOTE; if repeat imaging confirms PD due to any of the scenarios listed below, patients will be discontinued from study therapy.

In determining whether or not the tumor burden has increased or decreased, site study team should consider all target lesions as well as non-target lesions.

Scenarios where PD is confirmed at repeat imaging (iCPD):

- Tumor burden remains $\geq 20\%$ and at least 5 mm absolute increase compared to nadir
- Non-target disease resulting in initial PD is worse (qualitative)
- New lesion resulting in initial PD is worse (qualitative)
- Additional new lesion(s) since last evaluation

In patients who have initial evidence of radiological PD, it is at the discretion of the treating physician whether to continue a patient on study treatment until repeat imaging is obtained. This clinical judgment decision should be based on the patient's overall clinical condition, including performance status, clinical symptoms, and laboratory data.

iRECIST criteria include the above RECIST 1.1 derived criteria (see Table 11 and Table 12 below) with the proviso that the increase in tumor burden must be shown to increase, but in the case of iUSD, iUPR or iCR, the assessment time bar is reset.

For target lesions, iCR, iPR and iSD can all be assigned after iUPD has been documented as long as iCPD has not been confirmed. Progression is confirmed in the target lesion category if the next imaging assessment after iUPD (4-8 weeks later) confirms an increase in the sum of target lesions dimensions of greater than 5 mm. However, iCPD is not met if the imaging assessment after iUPD is followed by CR, PR or SD (compared to baseline as defined in RECIST 1.1). The status is reset and assessment continues. Please note this is different from RECIST 1.1

Thus iUPD can be assigned on multiple occasions, as long as iCPD is not declared.

Table 11 Comparison of RECIST 1.1, iRECIST and irRECIST

	RECIST 1.1	iRECIST	irRECIST
Definitions of disease: numbers, sites and target or non	Measurable are diameters greater than 10 mm (15 for nodes maximum of 5 (2 per organ))	No change from RECIST 1.1	No change from RECIST 1.1
CR, PR or SD	Cannot have met criteria for progression	Can have had iUPD (more than once) but not iCPD before iCR, iPR or iSD	Use of terminology based around RECIST 1.1
Confirmation of CR or PR	Only in non-randomized studies	As per RECIST 1.1	As per RECIST 1.1
Confirmation of SD	Not required	As per RECIST 1.1	As per RECIST 1.1
New lesions	Progression: recorded but not measured	iUPD but only becomes iCPD if on the next scan there are new lesions or the size increases by greater than 5 mm	Unclear
Confirmation of progression	Not required	Required	Required
Consideration of clinical status	Not required	Clinical stability considered at iUPD to decide treatment continuation	As iRECIST without terminology considering unconfirmed findings

Table 12 Trajectory of progression in iRECIST

Target Lesions: iCR, Non-target: iCR, no new lesions	iCR	iCR
Target lesions: iCR, Non-target: non iCR/non iUPD, no new lesions	iPR	iPR
Target Lesions: iPR, Non-target: non iCR/non iUPD, no new lesions	iPR	iPR
Target lesions: iSD, Non-target: non iCR/non iUPD, no new lesions	iSD	iSD
Target lesions: iUPD with no change or with a decrease from the last time point, Non-target: iUPD with no change or decrease from last time point, new lesions	NA	New lesions confirm iCPD if new lesions previously identified and increased in size (≥ 5 mm in sum of measures for new lesions or any increase for new lesion non-target) or increase in number. If no change is seen in new lesions assignment remains iUPD
Target lesions: iSD, iPR, iCR, non-target: iUPD, no new lesions	iUPD	Remains iUPD unless iCPD is confirmed by increase in the size of non-targets (does not need to meet RECIST 1.1 criteria)
Target lesions: iUPD, non-target: non iCR/non iUPD, no new lesions	iUPD	Remains iUPD unless iCPD confirmed on the basis of further increase ≥ 5 mm; otherwise stays as iUPD
Target lesions: iUPD, non-target: iUPD, no new lesions	iUPD	Remains iUPD unless iCPD confirmed on previously identified targets iUPD ≥ 5 mm or non-target iUPD

Target lesions: iUPD, non-targets: iUPD, new lesions	iUPD	Remains iUPD unless iCPD confirmed by increase of ≥ 5 mm previously identified target, or non-target or an increase in size or number of new lesions
Target lesions non iUPD or progression, non-targets: non iUPD or progression, new lesions	iUPD	Remains iUPD unless iCPD confirmed by increase in size or number of new lesions previously identified.

Target lesions, non-target lesions and new lesions are defined according to RECIST 1.1 criteria: if no pseudoprogression occurs, RECIST 1.1 and iRECIST categories for CR, PR and SD are the same. * Previously identified in the assessment prior to this time point. ‘I’ indicates immune responses assigned using iRECIST

Patients may receive study drugs treatment while waiting for confirmation of PD if they are clinically stable as defined by the following criteria:

- Absence of signs and symptoms indicating disease progression
- No decline in ECOG performance status
- Absence of rapid progression of disease
- Absence of progressive tumor at critical anatomical sites (e.g., cord compression) requiring urgent alternative medical intervention
- No requirement for intensified management of disease related symptoms exists, including analgesia, radiotherapy and palliative care

When feasible, patients should not be discontinued until progression is confirmed. This allowance to continue treatment despite initial radiologic progression takes into account the observation that some patients can have a transient tumor flare in the first few months after the start of immunotherapy, but with subsequent disease response. Patients that are deemed clinically unstable are not required to have repeat imaging for confirmation of progressive disease.

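### Protocol Section 9.1.4 gives two conflicting target-lesion rules for confirming immune progression (iCPD)

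*Protocol*

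**What the plan says.** **The list in Section 9.1.4.** The first scenario for confirmed progression at repeat imaging is a tumor burden still at least 20% "and at least 5 mm absolute increase compared to nadir". The note above it makes the consequence mandatory: "if repeat imaging confirms PD due to any of the scenarios listed below, patients will be discontinued from study therapy". The matching continuation condition lets treatment go on when the repeat burden is less than 20% above nadir and any new or non-target disease that caused the progression is stable or better.

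**The text after the list.** iRECIST is said to include those criteria "with the proviso that the increase in tumor burden must be shown to increase". For target lesions, progression is confirmed if the next assessment "confirms an increase in the sum of target lesions dimensions of greater than 5 mm". That sentence does not name the sum from which the increase is measured.

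**Table 12.** For progression in target lesions only, the entry is "Remains iUPD unless iCPD confirmed on the basis of further increase" of at least 5 mm, and the patient "otherwise stays as iUPD". A separate row covers target lesions in "iUPD with no change or with a decrease from the last time point" when new lesions are also present. There the new lesions decide; if they have not changed, the status remains iUPD.

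**What depends on it.** Under Section 9.1.5, sites use iRECIST for treatment decisions. Confirmed progression means discontinuation; if progression is not confirmed, the patient resumes or continues. That section sends readers to an imaging guide for detail. SAP 4.2 defers to protocol Section 9 for assessment rules and gives no iCPD threshold. SAP 4.2.3 analyses the independent radiologist's categories, made under an imaging charter.

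**The concern.** The two rules use different reference scans. The list compares the repeat scan with nadir and asks whether the excess persists. Table 12 compares it with the iUPD scan and asks whether there has been more growth. A sum that has held steady, grown a little or started to shrink since iUPD can therefore be iCPD under one and iUPD under the other.

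The first consequence is for treatment: the same scan leads to a mandatory stop or to continuation. Section 9.1.4 lets clinically stable patients continue because an early flare may be transient, yet the list can stop a patient whose flare is already receding.

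The second consequence is for exploratory endpoints: time to iCPD, duration of immune response, iBOR and the iRECIST response rate. The independent read does not fully protect these. Table 13 requires no more imaging after site-confirmed progression, so later scans that might have shown iSD or iPR may not exist.

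**Working it through.** The plan states no figure on this point, so there is none to reproduce. The check applies both rules to the same sums. All sums below are assumed.

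**Inputs.** N is the nadir sum, U the sum at iUPD and R the repeat sum. The 20% and 5 mm list thresholds come from Section 9.1.4, the further 5 mm from Table 12, and the entry condition from Table 9 (target progression is a rise of at least 20% from nadir, with no 5 mm floor). The list's first bullet is read as the target-lesion rule, because its other bullets deal with non-target and new lesions.

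**Formulas.**
- Entry to iUPD: U ≥ 1.20N
- List, iCPD: R ≥ max(1.20N, N + 5)
- Table 12, iCPD: R ≥ U + 5
- Discordant band: max(1.20N, N + 5) ≤ R < U + 5

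Because U ≥ 1.20N, U + 5 is never below the list threshold. Every Table 12 confirmation therefore also meets the list, and the conflict runs one way. A grid of whole-millimetre sums with nadirs of 10 to 200 mm found no exception.

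**Main example, N = 60, U = 75.** List threshold: max(72, 65) = 72. Table 12 threshold: 75 + 5 = 80. Sums from 72 to just under 80 mm get opposite labels, a band of 8 mm. Those below 75 mm have shrunk since iUPD.

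**Scan by scan, N = 50, U = 62.**

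| Repeat (mm) | From nadir | From iUPD | List | Table 12 |
|---|---|---|---|---|
| 59 | +18% | −3 | not iCPD | iUPD not confirmed |
| 60 | +20% | −2 | iCPD | iUPD |
| 62 | +24% | 0 | iCPD | iUPD |
| 66 | +32% | +4 | iCPD | iUPD |
| 67 | +34% | +5 | iCPD | iCPD |
| 68 | +36% | +6 | iCPD | iCPD |

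At 67 mm the confirmation sentence, which needs more than 5 mm, is not met if measured from iUPD. At 68 mm all three agree.

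**Width of the band.**
- Minimal entry, U = 1.20N: 5 mm when N ≥ 25 (N = 60: 72 to <77); otherwise (1.20N + 5) − (N + 5) = 0.2N (N = 20: 25 to <29, or 4 mm).
- Entry at +50%, U = 1.5N: 10 mm at N = 20 (25 to <35), 23 mm at N = 60 (72 to <95), 35 mm at N = 100 (120 to <155).

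**Effect on repeated iUPD.** For N ≥ 25, 1.20N ≥ N + 5. Under the list, any repeat sum that still meets target progression is then iCPD at once, so the Table 12 outcome of staying in iUPD could not arise from persisting target burden. Section 9.1.4 nevertheless allows iUPD more than once, and Example 7 in SAP Table 3 shows iUPD followed by a second iUPD without iCPD. That example does not say which lesions are involved, so it supports the point without proving it.

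**The case against.** **The section can be reconciled.** The proviso follows the list and expressly qualifies it. The proviso, the target-specific sentence and Table 12 all ask for growth, so the list bullet could be dismissed as loose drafting. This shows which rule was probably intended. But the proviso has no millimetre threshold or precedence statement, and it leaves the bullet, the mandatory stop and the continuation condition based on nadir in force.

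**Section 9.1.5 softens the stop.** A patient with confirmed progression, clinical benefit and no further increase in burden may continue after consulting the sponsor's medical monitor. This stands in part. In the main example it can reach repeat sums of 72 to 75 mm, but on its terms not those above 75 and below 80 mm. It is also an exception, whereas Table 12 needs none. Its wording may presuppose the list rule or may concern iCPD called on new or non-target lesions. The text does not say which, so it neither settles the rule nor supports restricting the exception.

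**Other documents may decide.** The imaging guide and charter may already choose one rule. That is a real limit on the practical impact, although the protocol would still contradict itself.

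**A stronger reading to avoid.** A reader might infer a third test from the clause that "iCPD is not met if the imaging assessment after iUPD is followed by CR, PR or SD", because it names baseline: a sum well above nadir could still be a partial response from baseline. The clause adds that these categories are as RECIST 1.1 defines them. Table 9 makes a 20% rise from nadir progression, and Table 11 says RECIST 1.1 response or stable disease cannot have met progression criteria. A third rule is not shown.

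**Conclusion.** The conflict holds. One section contains two operative target-lesion rules for iCPD, and the list confirms progression in cases where Table 12 does not. The discordant band is 8 mm in the main example; its width varies with nadir and the size of the flare. How many patients would fall in it cannot be derived from the documents.

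The reach is limited to site decisions to stop treatment and the exploratory, descriptively reported iRECIST endpoints. A reader might extend it to the primary result, but RECIST 1.1 assessment ends at first progression (SAP 4.2.3.7) and iCPD arises only afterwards. The primary response rate and the Simon decision rules are unaffected. Nor does Table 13 itself order a stop for the disputed scan: it refers to progression confirmed by iRECIST and sets no threshold. The stop comes from the list and its note. What Table 13 lacks is a row for a repeat scan that remains iUPD.

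The conclusion rests on the protocol and SAP text alone. Practical impact is uncertain until the imaging guide and charter are checked.

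**What to change.** Adopt one target-lesion definition, following Table 12.

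1. Replace the first bullet of the confirmation list with: *further increase of at least 5 mm in the target-lesion sum compared with the iUPD assessment*.
2. Replace the continuation condition of less than 20% above nadir with: *criteria for iCPD not met*.
3. In the confirmation sentence after the list, write *at least 5 mm compared with the iUPD sum*.
4. Add a row to Table 13 for a repeat scan that remains iUPD, following Section 9.1.5: a clinically stable patient may continue, with the next scan on the nine-week schedule. Align the imaging guide and charter.

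In the main example, 73 mm and 79 mm then remain iUPD and 80 mm is iCPD wherever the reader looks.

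The cost is wording only, with no change to readers or to the Simon design. The clinical downside is that growth of less than 5 mm per scan is confirmed later, so some patients stay on treatment longer. With a nadir of 60 mm and sums of 75, 79 and 83 mm, the list would confirm at 79 mm. Measured from the preceding iUPD scan, each rise is 4 mm and none of these scans confirms. Measured from the first iUPD, 83 − 75 = 8 mm confirms at the third scan. The new text should therefore say which iUPD scan is the reference when iUPD repeats.

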9.1.5 In Study iRECIST Assessment of Disease

As noted above, if tumor imaging shows initial disease progression, the study site may elect to continue treatment, repeat imaging 4-8 weeks later and assess tumor response or confirmed progression per iRECIST.

iRECIST is the adaptation of RECIST 1.1 as described below to account for the unique tumor response seen with immunotherapeutic drugs. iRECIST will be used by site investigator/local radiology review to assess tumor response and progression, and make treatment decisions. This data will be collected in the clinical database. Treatment efficacy based on iRECIST as assessed by central imaging vendor review will be

evaluated retrospectively.

Table 13 Imaging and treatment after first radiologic evidence of PD (iRECIST designation iUPD)

	Clinically Stable		Clinically Unstable	
	Imaging	Treatment	Imaging	Treatment
1st radiologic evidence of PD by RECIST 1.1	Repeat imaging at \geq 4 weeks at site to confirm PD	May continue study treatment at the local site Investigator's discretion while awaiting confirmatory tumor imaging by site by iRECIST.	Repeat imaging at \geq 4 weeks to confirm PD per physician discretion only	Discontinue treatment
Repeat tumor imaging confirms PD by iRECIST at the local site	No additional imaging required	Discontinue treatment (exception is possible upon consultation with sponsor)	No additional imaging required	N/A
Repeat tumor imaging shows SD, PR or CR by iRECIST by the local site	Continue regularly scheduled imaging assessments	Continue study treatment at the local site Investigator's discretion	Continue regularly scheduled imaging assessments	May restart study treatment if condition has improved and/or clinically stable per Investigator's discretion. Next tumor image should occur according to the every 9 week (63 \pm 7 days) imaging schedule

- In determining whether or not the tumor burden has increased or decreased, local study site investigators should consider all target lesions as well as non-target lesions. Subjects that are deemed clinically unstable are not required to have repeat tumor imaging for confirmation.
- For a **clinically stable** subject with first radiologic evidence of progressive disease by RECIST 1.1 (i.e., **unconfirmed progression of disease or iUPD**), it is at the discretion of the site investigator to continue treating the subject with the assigned treatment per protocol until progression of disease (iCPD) is confirmed at least 28 days from the date of the scan first suggesting PD. If radiologic progression is confirmed by subsequent scan then the subject will be discontinued from trial treatment. If radiologic progression is not confirmed by iRECIST per the site, then the patient should resume or continue trial treatment and have their next tumor imaging according to the protocol schedule of every 9 weeks (end of every 3rd treatment cycle) until progression is confirmed at a later timepoint by the site. In applying iRECIST, the appropriate documentation at

each time point must be made (i.e. iSD, iUPR, iUCR). For a more comprehensive and detailed account of the application of RECIST 1.1 and iRECIST for in-study imaging assessments please refer to the imaging guide document Note that RECIST 1.1 must always serve as the primary imaging assessment guide up to the first indication of disease progression after which iRECIST may be used as described.

- Any subject deemed **clinically unstable** should be discontinued from trial treatment at 1st radiologic evidence of PD and is not required to have repeat imaging for PD confirmation.
- In subjects who discontinue study therapy without documented disease progression, every effort should be made to continue monitoring their disease status by tumor imaging using the same imaging schedule used while on treatment (every 9 weeks), until (1) the start of new anti-cancer treatment, (2) disease progression (3) death, or (4) the end of the study, whichever occurs first.

If a subject has confirmed radiographic progression (i.e. 2 scans at least 4 weeks apart demonstrating progressive disease) per iRECIST, but the subject is achieving a clinically meaningful benefit, and there is no further increase in the tumor burden at the confirmatory tumor imaging, an exception to continue treatment may be considered following consultation with the Sponsor's Medical Monitor. In this case, if treatment is continued, tumor imaging should continue to be performed following the intervals as outlined in sections 6.0 Study Flowchart and be submitted to the central imaging vendor. iRECIST: for the sequences of imaging assessments following iUPD please see Table 11 and Table 12.

10 PHARMACODYNAMIC SAMPLING

Pharmacodynamic blood samples will be collected on Cycle 1 Day 1 before the dose of pembrolizumab and 4 hours post-birinapant dose and on Cycle 1 Day 2 at 24 hours post-birinapant dose. On Cycle 1 Day 8, pharmacodynamics blood samples will be collected before the dose of birinapant, and 4 hours post-birinapant dose. Refer to [Table 14](#).

Table 14 Timing of Pharmacodynamic Sampling

Birinapant Infusion (Cycle 1 Day 1)	
Sample 1	Prior to pembrolizumab infusion
Sample 2	4 hours after the end of the birinapant infusion
Birinapant Infusion (Cycle 1 Day 2)	
Sample 3	24 hours after completion of birinapant infusion
Birinapant Infusion (Cycle 1 Day 8)	
Sample 4	Prior to birinapant infusion
Sample 5	4 hours after the end of the birinapant infusion

Blood samples will be collected to evaluate changes in cIAP1 expression in pre- and post-treatment samples as a pharmacodynamic marker of birinapant activity. Blood samples (PBMCs) may also be evaluated for gene expression studies to understand the mechanism of action of the combination of birinapant and pembrolizumab.

Serum samples will be evaluated for cytokines such as GM-CSF, IFN γ , IL10, IL2, IL3, IL4, IL5, IL6, IL7, IL8, MIP-1 α , MIP-1 β , MCP-1, TNF α , and TNF β .

Paraffin embedded archival tumor tissue will be obtained if available from all patients for gene expression studies, immunohistochemistry for PD-L1 and cIAP1 expression and for assessment of Tumor Infiltrating Lymphocytes (TILs). In patients for whom a paraffin embedded archival tissue sample is not available, a pre-dose fresh tumor biopsy may be performed however this is not required for participation on the study, and patients without a paraffin embedded archival sample or a fresh biopsy may still be enrolled.

Patients may also consent to have an optional post-dose tumor biopsy at a single time-point any time during or after Cycle 2.

Translational biomarker assessments of blood, archival tumor samples and optional tumor biopsy samples will be evaluated (see [Table 15](#)). Pre- and post-treatment changes in the expression of cIAP1 in peripheral blood samples will be assessed. Pre-treatment PD-L1, cIAP1 and Tumor Infiltrating Lymphocytes (TILs) will also be evaluated in archival tumor samples and / or pre- and post-treatment optional tumor biopsy. Inhibitor of apoptosis protein (IAP) gene copy number studies in archival tumor samples or pre-treatment optional tumor biopsy samples will be conducted. Blood or serum samples may also be evaluated for cytokines such as GM-CSF, IFN γ , IL10, IL2, IL3, IL4, IL5, IL6, IL7, IL8, MIP-1 α , MIP-1 β , MCP-1, TNF α , and TNF β . CD3, CD4, CD8, and CD19 and FOXP3 as well as absolute neutrophil count and absolute lymphocyte count will be assessed through peripheral blood pre- and post-dosing of birinapant and pembrolizumab.

Table 15 Summary of Pharmacodynamic Assessments

Marker	Tissue	Purpose of analysis

Pre- and post-treatment levels of cIAP1 expression	Blood (PBMC)	Evidence of target engagement of birinapant
Gene expression analysis	Blood (PBMC)	Evidence of immune system modulation
Serum Cytokines such as GM-CSF, IFN γ , IL10, IL2, IL3, IL4, IL5, IL6, IL7, IL8, MIP-1 α , MIP-1 β , MCP-1, TNF α , and TNF β	Blood (serum)	Evidence of immune system modulation
Blood samples looking at CD3, CD4, CD8, and CD19 as well as absolute neutrophil count and absolute lymphocyte count	Blood	Peripheral changes in WBC populations
Pre-treatment PD-L1 expression	Archival tumor	May predict pembrolizumab sensitivity
Gene expression analysis by Nanostring	Archival tumor or pre-treatment optional biopsy	May predict pembrolizumab sensitivity. May allow derivation of predictive response signature of combination
	Post-treatment optional biopsy	Evidence of treatment-induced changes
cIAP1 expression	Archival tumor	May predict birinapant or combination sensitivity
	Post-treatment optional biopsy	Evidence of target expression and modulation in tumor
Inhibition of apoptosis protein (IAP) gene copy number	Archival tumor	May predict birinapant or combination sensitivity
Tumor infiltrating lymphocytes (TILs) CD3, CD4, CD8 and CD20 and FOXP3	Archival tumor	May predict birinapant or combination sensitivity
	Post-treatment optional biopsy	May provide evidence of increased anti-tumor immune activity
MSI mismatch repair assessment (CRC only)	Archival tumor	May predict pembrolizumab sensitivity

